6.4.1 Peri-Dosing AEs

The incidence of peri-dosing events (bradycardia, desaturation, and vomiting) will be summarized. In addition, the incidence of complications related to the placement of bi-nasal prongs (bleeding, apparent obstruction to the nares, occlusion of the prongs, nasal irritation, and other) will be summarized. Peri-dosing events and complications related to the placement of the prongs will also be summarized with all adverse events.

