5.2.5 Repeat Dosing

In order to ensure the safety of repeat dosing, specifically in regards to AEs and electrolyte changes (such as sodium and potassium levels), and to ensure subjects with a demonstrated need receive treatment, 1 repeat dose will be allowed for all dosing groups. The repeat dose will consist of repeating the same dose and will occur between 2 and 24 hours after the initial dose, if the repeat dosing criterion is met. The repeat dosing criterion is defined as at least 2 hours, but no more than 24 hours, after dosing and the subject must require a sustained need for supplemental oxygen at or above the qualifying FiO_2 level for study entry (ie, 0.25) for at least 30 minutes to maintain SpO_2 of 88% to 95%.

As with the initial dose, the IWRS will be used to receive the study drug assignments, and all other procedures that were performed for the initial dose will be followed for the administration of the repeat dose.

[figure not shown]
If, in the opinion of the PI, repeat dosing would compromise the safety of the subject, repeat dosing will not occur.

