8.2 Primary Observation Period

The following will be documented for each randomized subject during the Primary Observation Period of the study (≤ 48 hours after randomization [T_0]):

1. Date and time (T_0) of randomization and the study dosing group assignment (Section 5.2.2)
2. The date and time of the initiation and completion of aerosol delivery (Section 5)
3. All AEs, including ADEs (Section 9)
Peri-dosing events (defined as an AE with an onset time ≤ 2 hours from the time of initiating administration of lucinactant for inhalation) may include but not be limited to:
 - Bradycardia (as noted by HR < 100 bpm for ≥ 20 seconds) (Section 7.1.1)
 - Desaturation (as noted by O₂ saturation $< 80\%$ for ≥ 20 seconds) (Section 7.1.3)
 - Gagging/regurgitation
 - Apnea (central, obstructive, or combined) (Section 7.1.1)
 - Pallor
 - Complications related to placement of bi-nasal prongs (bleeding, apparent obstruction of the nares, bi-nasal prongs occlusion requiring removal and replacement, nasal irritation).
4. Respiratory support and supplemental oxygen as outlined in Section 7.6
5. nCPAP settings (Section 5.4), (Section 7.6)
6. FiO₂ values (Section 7.1.4)
7. Signs and symptoms consistent with worsening of respiratory status (Section 7.5)
8. Vital signs and SpO₂ (Section 7.1.1, Section 7.1.3)
9. PCO₂ values (Section 7.1.5)
10. Chest radiograph, as applicable (Section 7.1.8)
11. Gastric liquid volume (Section 7.1.9)
12. Serum electrolytes (Section 7.1.7)
13. Defecation (initial 24 hours following randomization) (Section 7.1.10)
14. Concomitant medications (Section 7.3)
15. Technical performance of the device (Section 5.1.4)
16. The use of pacifiers

8.3 Extended Observation Period:

The following assessments are to be performed during the Extended Observation Period of the study (> 48 hours to ≤ 7 days after date of randomization). Daily measurements are to be obtained as close to 0800 as possible.

1. Assessment and documentation of respiratory support and supplemental oxygen (Section 7.6)
2. Signs and symptoms consistent with worsening of respiratory status (Section 7.5)
3. Vital signs (Section 7.1.1)
4. SpO₂ (Section 7.1.3)
5. Chest radiograph, as applicable (Section 7.1.8)
6. Incidence of AEs, including ADEs (Section 9)
7. Concomitant medications (Section 7.3)

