- AEs and ADEs (including peri-dosing events and nasal excoriations)
- Air leak (especially pneumothorax and pneumomediastinum)
- Survival
- Use of respiratory support and supplemental oxygen
- Complications of prematurity
- Assessments of the following:
 - a) Arterial carbon dioxide (PCO₂)
 - b) Serum electrolyte measurements
 - c) Vital signs
 - d) Gastric liquid volume
 - e) Oxygen saturations (SpO₂)
- Chest radiography prior to intubation, if such a procedure does not delay or compromise the emergent care of the subject

A peri-dosing event is defined as an adverse event with an onset time ≤ 2 hours from the time of initiating administration of lucinactant for inhalation

Efficacy endpoints (exploratory objective) in the study include:

- Incidence of bronchopulmonary dysplasia (BPD) at 36 weeks PMA
- Rate of survival without BPD at 36 weeks PMA
- Technical performance of the ADS
- Worsening respiratory status either during or after exposure to lucinactant for inhalation
- Physiological parameters (eg, FiO₂, PCO₂)

The statistical analysis of both the primary and secondary safety and tolerability objectives will be based on all randomized preterm neonates in the study. In addition, data from all evaluable preterm neonates will be analyzed for efficacy signals as an exploratory endpoint. As this is an open-label study with no hypothesis testing, no adjustments for *p*-values are required or employed.

TABLE OF CONTENTS

EXECUTIVE SUMMARY	3
1 OVERVIEW.....	9
1.1 BACKGROUND.....	9
1.1.1 Treatment of Neonatal Respiratory Distress Syndrome	9
1.1.2 Development of Aerosolized Device for Lucinactant Delivery	10
1.2 OBJECTIVES	11
1.2.1 Primary Objective	11
1.2.2 Secondary Objective	11
1.2.3 Safety Evaluations	11
1.2.4 Exploratory Efficacy Objective	12
1.3 HYPOTHESES.....	13
2 INVESTIGATIONAL PLAN	14
2.1 STUDY POPULATION	14
2.1.1 Inclusion criteria	14
2.1.2 Exclusion Criteria	14
2.2 STUDY DESIGN AND RANDOMIZATION.....	15
2.2.1 Treatment Groups	16
2.2.2 Repeat Dosing	16
2.2.3 Sample Size Justification	17
2.2.4 Study Schedule	18
3 STUDY SUBJECT CHARACTERISTICS.....	19
3.1 DEMOGRAPHICS AND BASELINE CHARACTERISTICS	19
3.1.1 Demographics	19
3.1.2 Birth and Maternal History	19
3.2 SUBJECT DISPOSITION	19
3.3 STUDY AND CONCOMITANT MEDICATION.....	20
3.3.1 Compliance	20
3.3.2 Number of Doses	20
3.3.3 Previous and Concomitant Medication	20

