1.2.3 Safety Evaluations

The following measures are to be documented in the electronic case report form (eCRF) in accordance with timings outlined in study schedule:

1. Survival (date and time of death if applicable)
2. AEs, including ADEs
 - To include: nasal excoriations by examination (≥ 24 hours to ≤ 7 days following aerosol exposure) and evidence of lung air leak (especially pneumothorax)
 - To be categorized as a peri-dosing events if onset of event is ≤ 24 hours from the time of initiating administration of lucinactant for inhalation
3. Signs consistent with worsening respiratory status
4. Concomitant medications
5. Use of respiratory support and supplemental oxygen to include:

- Need for endotracheal intubation and mechanical ventilation
 - Need for intermittent positive pressure breaths using inflating pressures above the set CPAP pressure administered manually or mechanically through any patient interface
6. nCPAP and fraction of inspired oxygen (FiO₂) requirements
 7. Complications of prematurity (ie, IVH, periventricular leukomalacia [PVL], pulmonary hemorrhage, NEC, patent ductus arteriosus [PDA], sepsis, ROP, BPD)
 8. Physical examinations
 9. Tolerability of lucinactant for inhalation
 10. Incidence leading to withdrawal from study
 11. Incidence of air leak
 12. Assessments of the following:
 - a) PCO₂
 - b) Serum electrolyte measurements
 - c) Body weight
 - d) Vital signs
 - e) Gastric liquid volume
 - f) Defecation
 - g) Oxygen (O₂) saturation, as determined by pulse oximetry (SpO₂)
 - h) Chest radiography, as applicable

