2.2.2 Repeat Dosing

In order to ensure the safety of repeat dosing, specifically in regards to AEs and electrolyte changes (such as sodium and potassium levels), and to ensure subjects with a demonstrated need receive treatment, 1 repeat dose will be allowed for all dosing groups. The repeat dose will

consist of repeating the same dose, and will occur between 2 and 24 hours after the initial dose, if the repeat dosing criterion is met. The repeat dosing criterion is defined as: at least 2 hours, but no more than 24 hours, post dosing and a FiO_2 level of at least 0.35.

If, in the opinion of the PI, repeat dosing would compromise the safety of the subject, repeat dosing will not occur.

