6.3 EXTENT OF EXPOSURE

All subjects randomized to active treatment are to receive one dose of study medication. Subjects will receive 30, 45, 60, or 90 minutes of aerosolized lucinactant. The number of subjects who

receive a repeat dose and the number of subjects whose study treatment is terminated early will be summarized.

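### SAP 6.4.1 and Table 6.1 give one peri-dosing incidence per dose level, leave the window and denominator undefined for infants dosed twice, and so never show events after the repeat dose.

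*SAP*

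**What the plan says.** **The window.** Protocol 8.2 defines a peri-dosing event as one with an "onset time ≤ 2 hours from the time of initiating administration of lucinactant for inhalation". Protocol 3.3, protocol Appendix 2, the SAP executive summary and the SAP schedule footnote also use 2 hours. SAP 1.2.3 differs: "To be categorized as a peri-dosing events if onset of event is ≤ 24 hours from the time of initiating administration". None of these texts says whether the first administration is meant or each one.

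**The repeat dose.** SAP 2.2.2 states that "1 repeat dose will be allowed for all dosing groups". Protocol 5.2.5 introduces the same provision with "In order to ensure the safety of repeat dosing, specifically in regards to AEs and electrolyte changes", alongside treating infants with a demonstrated need. It adds that the procedures used for the initial dose also apply to the repeat.

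**The analysis.** SAP 6.4.1: "The incidence of peri-dosing events (bradycardia, desaturation, and vomiting) will be summarized". SAP 6.4 sets frequency and percent by treatment group, and SAP 2.2.1 defines treatment group as each active dose plus the combined controls. Dose number is not part of it. Table 6.1 is the only peri-dosing table.

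**Use of repeat-dose status.** It is only counted. SAP 3.3.2 and Table 3.2 give the number of treatments, and SAP 6.3 says that the number of subjects who "receive a repeat dose and the number of subjects whose study treatment is terminated early will be summarized".

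**The concern.** The window is anchored to starting an administration, and an infant may have one or two of them. One percentage per dose level therefore has no settled meaning until the plan says which administrations count and what they are divided by.

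Repeat dosing follows continued oxygen need, so its frequency may differ between dose levels. The repeat criterion also has different FiO₂ thresholds in the two documents (0.25 in protocol 5.2.5, 0.35 in SAP 2.2.2). They must be reconciled, and how often a repeat is given depends on which applies. If events in both windows are pooled per infant, a dose that is repeated more often shows more peri-dosing events at the same risk per administration. If only the first window counts, events after the repeat dose are absent from the table.

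At stake is what the trial can say about tolerability of the repeat dose, and how cleanly the peri-dosing rates feed the secondary objective (maximum tolerated dose) and dose selection.

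**Working it through.** The documents give no figure on this point, so there is none to reproduce. They also give neither the risk per administration nor the repeat fraction. Both are assumed below and shown as ranges.

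**1. Observed time, 2-hour definition.** The protocol synopsis and the SAP executive summary allow the repeat from 2 hours after completion of the initial dose. With aerosol times of 30 to 90 minutes, the repeat starts at least 0.5 + 2 = 2.5 h (Group I) to 1.5 + 2 = 3.5 h (Group IV) after the first start. The first window has closed by then. If the window restarts, observed time is 2 + 2 = 4 h against 2 h.

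**2. Observed time, 24-hour wording (SAP 1.2.3).** The windows can overlap. The earliest repeat in Group I gives 24 + 2.5 = 26.5 h in all; a repeat starting 24 h or more after the first start gives 48 h. The ratio to one window is 26.5/24 = 1.10 up to 48/24 = 2.0.

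**3. Per-infant incidence if the window restarts.** Let p be the risk per administration, the same for both doses and unrelated to who gets a repeat, and let r be the fraction given a repeat. With independent administrations, an infant dosed twice has risk 1 − (1 − p)² = p + p(1 − p). The group value is p + r·p(1 − p), an excess over p of r(1 − p) in relative terms.

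| p | r = 0.25 | r = 0.50 | r = 0.75 |
|---|---|---|---|
| 0.10 | 12.3% (+23%) | 14.5% (+45%) | 16.8% (+68%) |
| 0.20 | 24.0% (+20%) | 28.0% (+40%) | 32.0% (+60%) |
| 0.40 | 46.0% (+15%) | 52.0% (+30%) | 58.0% (+45%) |

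**4. Correlation within infant.** With correlation ρ between the two outcomes, the excess is multiplied by (1 − ρ). For p = 0.20 and r = 0.50, ρ = 0.5 gives 0.20 + 0.50 × 0.16 × 0.5 = 24% instead of 28%. At ρ = 1 the excess is zero.

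**5. A pooled figure cannot locate the risk.** If all infants are dosed twice, a first-dose risk of 0.10 with a repeat-dose risk of 0.30 gives 1 − 0.90 × 0.70 = 37%. A risk of 0.20 at both gives 1 − 0.80² = 36%.

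**6. Can the order of doses change?** Lower dose p = 0.20, r = 0.75: 0.20 + 0.75 × 0.16 = 32.0%. Higher dose p = 0.25, r = 0.25: 0.25 + 0.25 × 0.1875 = 29.7%. Out of 8 infants that is 2.56 against 2.38, a gap of about 0.2 of an infant. One infant is 12.5 percentage points, and the standard error of each percentage is about √(0.3 × 0.7/8) = 16 points.

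**7. If the window does not restart.** The arithmetic in steps 3 to 6 does not apply. The repeat starts after the 2-hour window has closed, so no event after it can count as peri-dosing under that definition.

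**8. Is the split available elsewhere?** The SAP's planned listings cover deviations, deaths, serious events, early termination, medications, ventilation and oxygen. There is no general adverse event listing and no table by dose number, so non-serious events after the repeat dose cannot be recovered from the planned outputs.

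**The case against.** **Nothing says per infant or per administration.** This stands. SAP 6.4 names no denominator, and the once-per-subject counting rule in SAP 6.4.3 is worded for other adverse events. A reader might infer that the plan definitely reports per infant and that infants dosed twice definitely have double the observed time. The documents do not support that: both links are inferences, and the doubling also needs the 2-hour text to prevail over the 24-hour text.

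**Per-infant incidence is a legitimate quantity.** This also stands. The assigned regimen is a dose with a possible repeat, and the safety review committee advises on moving to the next level on that basis. An any-administration rate answers that question and should be kept. It cannot, however, describe the repeat dose itself.

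**Repeat-dose safety is not a listed objective.** Correct; it is a stated reason for the provision. A reason that names adverse events still calls for a summary that shows them.

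**The trial makes no comparison.** SAP 6.4 rules out comparing adverse events between groups, and there are no hypothesis tests. Yet SAP 1.1.2 and 2.2.3 say the results help select doses, so the columns will be read side by side.

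**A split adds little at this size.** With r = 0.25 to 0.75, the repeat-dose denominator is 2 to 6 infants per dose. With 0 events in 4, the one-sided 95% upper bound is 1 − 0.05^(1/4) = 52.7%. Repeat recipients are selected by oxygen need. Both limits stand and make the split descriptive only.

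**The committee sees all adverse events anyway.** This partly mitigates the gap during the trial, but does not supply the final tables.

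**Conclusion.** The gap is real and modest. On either reading of the window, no planned table shows peri-dosing events after the repeat dose. That conclusion needs no assumed numbers.

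The mixing of risk with repeat frequency is conditional. It requires a window that restarts (supported by protocol 5.2.5 but not written in the definition) and a per-infant denominator (implied by SAP 6.4). Under those readings, with p = 0.1 to 0.4, r = 0.25 to 0.75 and independent administrations, incidence exceeds the per-administration risk by 15% to 68%, and by less if events are positively correlated within infant.

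A reader might go further and infer that the table will reverse the true order of the doses. The documents give neither p nor r, and the example in step 6 needs opposite repeat fractions at the two doses. Its gap of 0.2 of an infant is far below what 8 infants per group can show. Reversal is possible in principle; it is not a demonstrated distortion.

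**What to change.** 1. Reconcile SAP 1.2.3 (24 hours) with the 2-hour definition used elsewhere in the SAP and in the protocol.
2. State in SAP 6.4.1 that the window applies to each administration, and name the denominator.
3. In Table 6.1, within each dose level, show infants with an event after the first administration over infants who started it, and infants with an event after the repeat administration over infants who started that one. Keep a per-infant row for any administration.
4. Add a note that the first-versus-repeat split is descriptive, because the repeat denominators are small and those infants are selected by oxygen need.

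The cost is one clarified definition and two extra columns in one table, with no new data: aerosol start times (protocol 8.2) and adverse event onset times (protocol 9) are already recorded. The change should be made before database lock, the point by which the SAP intends its methods to be fixed.

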6.4.2 Other AEs Related to Surfactant Administration

Individual air leaks (e.g., pneumothorax, pulmonary interstitial emphysema, pneumomediastinum, pneumopericardium, and subcutaneous emphysema) will be identified by medical review of all AEs and summarized by treatment group.

6.4.3 Other AEs

AEs, other than those listed above, will be summarized by the MedDRA preferred term and SOC for all AEs, regardless of relationship to study drug, and for AEs at least remotely related. If an AE occurs multiple times for the same subject within the same term or body system, only the most severe occurrence for that term or body system will be counted.

In addition, all AEs will be summarized by severity (mild, moderate, severe), relationship to the study drug (unrelated, unlikely related, possibly related, definitely related), whether or not the AE was device related, gender, race, and ethnic origin.

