There appeared to be a higher rate for several AEs, including airleak, in the Group I active group compared with the control group; however, small numbers make these comparisons difficult. Moreover, data for Dosing Groups II, III, and IV do not suggest clinically relevant areas of concern. The most common type of air leak reported has been pneumothorax. No clinically relevant differences have been observed between the active groups and the control group on completion of dosing Groups II, III, and IV.

The subjects in the active and control groups exhibit results for serum electrolytes that are very similar, indicating that the investigational product has had no demonstrable impact on serum electrolytes.

In summary, the preliminary data for Protocol 03-CL-1201 indicate that there are no specific safety concerns and that the doses studied are generally safe and tolerated. The SRC has reviewed all safety data from Dosing Groups I through IV, and in each case recommended that the study continue. The results also indicate that the dose of 25 mg TPL/kg is likely a subtherapeutic dose. After evaluation of the data by the steering committee and discussion with Discovery, it was determined that the appropriate starting dose of for this study (03-CL-1401) should be 50 mg TPL/kg.

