1.3 HYPOTHESES

This study has no hypothesis tests.

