2.2.3 Sample Size Justification

The number of subjects randomized (8 in each active group and 8 in each control group) is considered sufficient to establish safety and tolerability before proceeding to the next higher dose. A total of approximately 32 subjects assigned to the active arm and approximately 32 subjects for the control arm for the entire study is considered sufficient to assess the overall safety and tolerability and to select safe and well-tolerated doses. Statistical sample size calculations were not performed.

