6.4 ADVERSE EVENTS

All AEs will be coded by preferred term and system organ class (SOC) from the Medical Dictionary for Regulatory Activities (MedDRA), version 16.1 or above, and will be reviewed by the medical monitor or designee. All AEs will be summarized as categorical variables (frequency and percent) by treatment group unless otherwise indicated. AEs that are related to the device (ADEs) will be summarized with all AEs and separately. AEs will not be compared between treatment groups.

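### SAP 6.4.3, as worded, leaves air leaks out of the SOC/preferred-term AE summaries and contradicts 6.4.1 on peri-dosing events

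*SAP*

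**What the plan says.** SAP 6.4 sets the general rule: "All AEs will be summarized as categorical variables (frequency and percent) by treatment group unless otherwise indicated".

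SAP 6.4.1 gives peri-dosing events (bradycardia, desaturation, vomiting) and nasal-prong complications a summary of their own. It ends: "Peri-dosing events and complications related to the placement of the prongs will also be summarized with all adverse events".

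SAP 6.4.2 covers air leaks, which "will be identified by medical review of all AEs and summarized by treatment group". It says nothing about whether they also enter the overall AE summary.

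SAP 6.4.3 then begins: "AEs, other than those listed above, will be summarized by the MedDRA preferred term and SOC for all AEs". The sentence goes on to name two levels of summary: AEs whatever their relationship to study drug, and AEs with at least a remote relationship. Its second paragraph asks for summaries of all AEs by severity, relationship and device relation, with no exclusion.

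The SAP Executive Summary defines a peri-dosing event as an "adverse event with an onset time ≤ 2 hours from the time of initiating administration of lucinactant for inhalation".

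**The concern.** Safety against nCPAP alone is the primary objective, and the SOC/preferred-term tables are the central AE display for it. A rule that removes named event types from those tables should be deliberate and stated once. Here the rule conflicts with a neighbouring section for one group of events and stands unopposed for another.

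The unopposed case matters more. The SAP Executive Summary lists air leak as a key safety endpoint. Protocol Section 9 makes it an AE of special interest within the primary observation period. On the predecessor study, Protocol 2.2.3.2 reports: "There appeared to be a higher rate for several AEs, including airleak, in the Group I active group compared with the control group". The same paragraph cautions that the numbers are small and says Groups II to IV gave no clinically relevant concern. Even so, a reader would expect to find air leak in the main AE table.

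**Working it through.** There is no planned figure to reproduce. SAP 1.3 states "This study has no hypothesis tests" and SAP 2.2.3 states "Statistical sample size calculations were not performed". The check is a comparison of sections, followed by a short calculation of scale.

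**Step 1: what is excluded.** Within SAP 6.4, the events listed before 6.4.3 are those of 6.4.1 and 6.4.2.

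**Step 2: what each instruction does with them.**

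| Event | Own summary | Put back with all AEs? | First sentence of 6.4.3 | Second paragraph of 6.4.3 |
|---|---|---|---|---|
| Peri-dosing events | 6.4.1, Table 6.1 | Yes, end of 6.4.1 | Excluded | Included |
| Prong complications | 6.4.1 | Yes, end of 6.4.1 | Excluded | Included |
| Air leaks | 6.4.2, Table 6.2; also 6.5.8, Table 7.8 | No sentence | Excluded | Included |

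The first two rows contain a direct contradiction. In the third row the exclusion is not reversed. The general rule in 6.4 does not rescue it, because that rule applies only unless something else is indicated, and 6.4.3 can be read as indicating something else.

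**Step 3: effect on the tables.** Table 6.3.1 (SOC and preferred term) matches the first sentence of 6.4.3, so it would omit air leaks. Tables 6.3.2 and 6.3.4 match the second paragraph, so they would include them. Table 6.3.3 (SOC, preferred term and relationship) answers to both: the first sentence restricts the related-AE summary, and the second paragraph does not. The text does not say which applies. Totals could therefore differ between Table 6.3.1 and Table 6.3.2 for the same infants.

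**Step 4: scale.** One infant is 1/8 = 12.5 percentage points of an active-dose column and 1/32 = 3.1 points of the combined-control column. In Table 6.3.1 every air-leak preferred-term row would be empty. The any-AE row falls by the number of infants whose only AE is an air leak. The related-AE row falls by those whose only related AE is one.

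The plan gives no expected air-leak rate. As an assumption, take the pneumothorax rates that Protocol 1.1.1 cites from a large trial of nCPAP against intubation in very preterm neonates, 3% (intubation) to 9% (nCPAP):

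- 64 × 0.03 = 1.9 infants
- 64 × 0.09 = 5.8 infants

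About 2 to 6 infants in the whole study would then have a pneumothorax missing from Table 6.3.1. Other types of air leak would add to this. The fall in the any-AE row could be smaller, since many of these infants will have other AEs.

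**Step 5: direction.** The air-leak omission depends on event type, not arm, so the same rule applies to active and control infants. Peri-dosing status depends on the start of lucinactant, so only a treated infant can have it. A one-sided loss would need 6.4.3 to be followed over the last sentence of 6.4.1.

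**The case against.** The strongest case for leaving the text alone is that its intent is clear. Section 6.4.1 specifically includes peri-dosing and prong events, and a specific sentence should prevail over a loose opening phrase in a section headed as other AEs. The first sentence of 6.4.3 itself speaks of all AEs, its second paragraph has no exclusion, and the titles of Tables 6.3.1 to 6.3.5 carry none. Air leak is shown by treatment group in Tables 6.2 and 7.8, and a serious air leak also falls under the SAE summaries in 6.4.4. Nothing is hidden.

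Most of this stands for peri-dosing and prong events: the explicit text returns them, and what remains is a conflict to tidy. It does not settle air leaks. The reference to all AEs in 6.4.3 more naturally names a relationship level within the restricted set than cancels the restriction, and a table title does not define its contents. Tables 6.2 and 7.8 show air leaks but do not correct the totals in Table 6.3.1. For Table 6.2, the SAP does not say that relationship to study drug will be shown.

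A reader might infer something stronger: that the plan removes early bradycardia and desaturation from the active arm, keeps them in controls, and so flatters lucinactant. The documents do not support that. The last sentence of 6.4.1 puts those events back, and the listed events could also be read as event types, which would apply to both arms. Nor would the related events vanish from the report, since the second paragraph of 6.4.3 covers all AEs by relationship.

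**Conclusion.** Wrong as written, minor. The opening exclusion in SAP 6.4.3 conflicts with 6.4.1 for peri-dosing events and prong complications. Read literally, it also removes air leaks in both arms from Table 6.3.1 and the related-AE SOC/preferred-term summary. The consequence is tables that do not agree with each other, and any-AE and related-AE counts that are too low by the infants with no other qualifying event. The events themselves stay visible elsewhere in the report. No bias towards the active arm is shown; it would arise only if 6.4.3 overrode 6.4.1 and the exclusion went by onset window.

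This rests on two assumptions. First, a programmer follows the first sentence of 6.4.3 as written. Second, controls are in these tables, as 6.4 and the definition of treatment group in 2.2.1 imply. The safety population in 6.1 is worded around receipt of study medication and, read literally, would leave controls out; that is a separate point. The 2 to 6 infants further assume that the cited pneumothorax rates carry over to this population.

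**What to change.** Make three wording changes in the SAP:

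1. In the first sentence of 6.4.3, delete the exclusion set between commas after the opening word.
2. State that Tables 6.3.1 to 6.3.5 include every AE in both arms, peri-dosing events, prong complications and air leaks among them, and that Tables 6.1 and 6.2 are additional breakouts of the same events.
3. Add to 6.4.2 a sentence, parallel to the one that closes 6.4.1, saying that air leaks are also summarized with all adverse events.

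The cost is SAP text only. No new data and no new tables are needed.
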